The intervention consists of two parts, Options Counseling (OC) and Health Education (HE). The OC part includes family assessment, counseling and provision of emotional support, access assistance, and development of independent-living plans (care plans) using the Iowa's Heritage Area Agency on Aging database. The Options Counselor is trained to use motivational interviewing techniques to develop family care plans, provide emotional support, and connect families to available services and programs in the community. The HE part includes post-diagnosis family education using the 7-module health education toolkit developed specifically for this study based on the literature and expert reviews. OC-HE will conduct initial assessment to determine educational needs within 2 weeks of participant's randomization into the intervention group and develop initial care plan; and will conduct 5 monthly follow-up calls to adjust the care plan and provide educational components appropriate at each point. This intervention aims to create direct links between the medical clinics, home and community-based services (HCBS), and family.

Participants assigned to the usual care control group will participate in baseline, as well as 3- and 6-months

follow-up surveys. Those in usual care group will receive a general informational brochure from the Alzheimer's Association, and will be given an option of receiving a call from their local Options Counselor after completing the 6-month survey.

Study duration is about 18 months. We aim to start participant enrollment in August, 2019, complete recruitment by September, 2020, and complete data collection by March 2021. Each participant will be enrolled in this study for about 6 months from enrollment to final interview.

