Clinical teams led by project collaborators (Drs. [name], [name], and [name]) will review electronic medical records (EMRs) and use their existing knowledge of the patient to determine which days a diagnosis may be made. For those patients who have been diagnosed within the past 6 months from the beginning of the study, who are eligible for the study, the research team will be notified by clinical teams when those patients and their caregivers will be at the clinic for a visit. On the identified days, a member of the research team will be present at the clinic. In this case, the clinical team members will notify the research team about cancellations and last minute appointments. If a research team member cannot be present due to logistical difficulties, the clinical staff will give study flyer to the potential participants. If the potential participant indicates interest, a potential participant packet that includes the flyer, a consent letter, and study information sheet will be handed out. If the potential participant gives permission for research staff to contact them, the potential participant will be asked to fill out a contact form indicating their name and phone number or e-mail address that will be sent to the research staff from the clinical team staff. If the potential participant does not wish to provide contact information, they will be asked to call the research office indicated on the flyer.

There is no signed consent document for this study. There is a consent letter that interviewers will read through with the participant before the baseline interview begins. Since the study has rolling enrollment, caregivers will have up until the last 6 months of the study to participate (to allow participants enough time to receive the entire intervention). Eligibility will be confirmed by the research assistant before reading through the consent letter with the participant.

Anticipate Accrual Rate

- 25% of planned enrollment (26 participants) recruited by 09/30/2019

- 50% of planned enrollment (53 participants) recruited by 01/31/2020
- 75% of planned enrollment (80 participants) recruited by 04/30/2020
- 100% of planned enrollment (106 participants) recruited by 08/15/2020

Participant Retention

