Building a Bridge (between clinical and community care): Post-diagnosis support for persons with dementia and their families

Grant Number: 1R21AG056716-01A1

National Clinical Trial (NCT) Identified Number: NCT03932812

Principal Investigator: [name]

Sponsor: University of Iowa College of Public Health

Funded by: National Institute on Aging (NIA)

Revised Analytic Plan

[figure not shown]
January 2022

Building a Bridge Data Analyses Plan

Overview of the Intervention. Building a Bridge: a post-diagnosis support of persons with dementia and their family aims to assist community dwelling individuals newly diagnosed with dementia and their families to prepare them for community-based care and connect them to the services provided by the local Area Agency on Aging. The intervention consists of two components, Options Counseling (OC) and Health Education (HE) – the OC-HE intervention. Families receive standard OC services provided through the Iowa's Area Agencies on Aging that include a family assessment, counseling and provision of emotional support, access to community resources and supports, and development of independent-living plans (family action plans). The HE component involves the provision of post-diagnosis education using the educational modules specifically developed for this project to address the needs of families who recently received the diagnosis. The intervention contains 8 modules to support successful role transitions for patients and family: overview of dementia (e.g., symptoms, stages, management, things to consider after diagnosis), anticipating changes and challenges, social relationships and daily life, interacting with providers, addressing future needs, dementia and driving, elder mistreatment, and pandemic-related challenges. The module on social relationships and interactions focus on enhancing social support through the discussion of strategies to elicit positive support from network members.

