Interventions are ongoing and flexible to meet the needs of the individual family. Following the standard OC protocol, the family receives an initial telephone intervention (previously in-person home visit, but occurred over the phone due to the pandemic) by the interventionist. During the initial call, the OC uses assessment tool to identify caregiver/family needs and develop family action plans to connect families directly to services and programs available in the area. The interventionist also conducts an assessment to determine educational needs, then conducts 2 additional monthly follow-up calls to adjust the care plans and to provide educational components appropriate at each point (3-month intervention). This program, thus, creates direct links between the medical clinics, HCBS, and family. The OC tailors the information provision to meet the needs of those receiving it by providing additional information as the time progresses, allowing the recipients to identify their concerns at the moment and presenting materials to address expressed concerns. Participants receive all educational materials and a brief overview of contents at the end of the 3-months intervention period, including the topics that may not have been covered in great detail during the intervention calls. The Area Agency on Aging provides continued support to individuals who need their services after the completion of the intervention.

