Perceived support: At each assessment, the participants report their relationships with each network member (e.g., who provides emotional support? Who helps you provide direct care? Who participates in discussions to make care decisions) to assess network functions. Levels of support can be determined by taking an average support levels among family, non-family, professionals, for each type of support (e.g., emotional, informational, instrumental, direct care, care decision making).

Social engagement: Participants identify network members with whom they engage in social activities to assess how the network functions as a context for social engagement.

At the patient level, generalized linear models (GLM) with an appropriate link function (e.g., the identical link for continuous outcomes, the logit for dichotomous outcome, and the log link for count outcomes) will be used to assess associations between the caregiver and patient outcomes and network composition and network functions. In particular, a set of the composition measures will be considered as independent variables to each outcome in a GLM. Similarly, a set of network functions (e.g., change between baseline and 3-month) will be included to assess the association with each outcome at 6-month in a GLM.

Follow-up analyses

Once we identify network functions that are important for the caregiver and patient outcomes (e.g., emotional support, provision of direct care support) are identified in the main analyses, we will be able to conduct dyad-level analyses to identify the whole network characteristics (e.g., network size, homogeneity), network member characteristics (e.g., gender, relationships, live locally), as well as relationship characteristics (e.g., presence of trust, duration of relationship) that may contribute to such positive network functions.

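### The SAP's patient-level network models have no calendar-period term; if enrolment straddled March 2020, a pandemic shift could appear as a network association, though on planned accrual the distortion is small.

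*SAP*

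**What the plan says.** **Intervention.** The SAP (Overview of the Intervention) says the first contact was "previously in-person home visit, but occurred over the phone due to the pandemic". It lists eight modules, ending with "dementia and driving, elder mistreatment, and pandemic-related challenges". Protocol section 2.0 describes "post-diagnosis family education using the 7-module health education toolkit". The follow-up schedule also differs. Protocol section 2.0 says the interventionist "will conduct 5 monthly follow-up calls to adjust the care plan", and the SAP says the interventionist "then conducts 2 additional monthly follow-up calls to adjust the care plans". The SAP gives no reason for that change, so it is not counted here as a pandemic effect.

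**Accrual.** Protocol section 2.0 plans enrolment from August 2019 to September 2020. Section 5.0 sets milestones of 26 by 30 September 2019, "50% of planned enrollment (53 participants) recruited by 01/31/2020", 80 by 30 April 2020 and 106 by 15 August 2020. It expects 80 participants after 25% attrition. Neither document gives actual enrolment dates.

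**Analysis.** Under the SAP's Revised Data Analysis Plan, the patient-level GLMs take as regressors either a set of network composition measures or a set of network functions. The example given for functions is change from baseline to 3 months, with the outcome at 6 months. Social engagement is one network measure: "Participants identify network members with whom they engage in social activities". These models name no other covariate. The dyadic GEE under Follow-up analyses lists covariates only as examples, none of them calendar time. The SAP speaks of associations when it defines the GLMs and of mechanisms of influence when it explains their purpose. It refers to caregiver and patient outcomes without naming them. Burden and emergency care use come from Protocol section 1.0.

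**The concern.** These models compare caregivers whose networks differ. Allocation was randomised, but network size, support and social engagement were not. With rolling enrolment, caregivers seen before and during the pandemic may differ in both networks and outcomes for reasons that have nothing to do with a network mechanism. Restrictions could plausibly reduce engagement and help from outside the household. They could also raise burden and lower emergency visits. If so, lower engagement would go with higher burden, which inflates an apparent protective effect. It would also go with fewer visits, which hides one. The SAP acknowledges the pandemic when it describes the intervention but not in the models.

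**Working it through.** **Inputs.** Milestones and n = 80 are from Protocol section 5.0. The assumptions are accrual from 1 August 2019, linear between milestones; a pandemic start of 15 March 2020; a one-time drop in networks of d_x within-period SD; and a rise in burden of d_y SD. The true network effect is zero. No document gives a shift, so a range is shown.

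**Step 1: who is affected, on planned accrual**
- Enrolled by 15 March 2020: 53 + 27 × 44/90 = 66.2, leaving 39.8 of 106 with baseline in the pandemic.
- Enrolled by 15 December 2019 (3-month visit before 15 March): 26 + 27 × 76/123 = 42.7, leaving 63.3 with the 3-month visit in the pandemic.
- Enrolled by 15 September 2019 (6-month visit before 15 March): 26 × 45/60 = 19.5, leaving 86.5 with the 6-month outcome in the pandemic.
- Change score shifted (baseline before, 3-month visit after): 66.2 − 42.7 = 23.5 of 106. Later enrollees already start low and show no such change.

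Scaled to 80, these are about 30 (baseline), 48 (3-month), 65 (6-month) and 18 (change score).

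**Step 2: formula.** Let p_x and p_y be the proportions with the network measure and the outcome shifted. Everyone in the first group is also in the second, so without a period term:
- covariance C = d_x·d_y·p_x(1 − p_y)
- V_x = 1 + d_x²·p_x(1 − p_x), and V_y likewise
- spurious slope = −C/V_x; r = C/√(V_x·V_y)
- false-positive rate ≈ Φ(−1.96 + r√80) + Φ(−1.96 − r√80)

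Example, 6-month level with equal 0.8 SD shifts: p_x = p_y = 65/80 = 0.8125. C = 0.64 × 0.8125 × 0.1875 = 0.0975 and V_x = V_y = 1.0975. The slope is −0.089, r√80 = 0.795, and the false-positive rate is about 12%.

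**Step 3: false-positive rate for burden, no period term**

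| Network measure | 0.3 / 0.2 SD | 0.5 / 0.4 SD | 0.8 / 0.6 SD | 0.8 / 0.8 SD |
|---|---|---|---|---|
| 0-3-month change | 5.0% | 5.1% | 5.3% | 5.5% |
| Baseline level | 5.0% | 5.2% | 5.9% | 6.5% |
| 3-month level | 5.0% | 5.4% | 7.2% | 8.8% |
| 6-month level | 5.1% | 5.8% | 9.3% | 12.5% |

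Columns give d_x / d_y. Simulation agrees to within about half a percentage point. With a three-category period term (before, straddling, within) it returns about 5% throughout.

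**Step 4: emergency visits.** This uses a Poisson model with an assumed pre-pandemic mean of 0.6 visits and 25-40% fewer visits in the pandemic. On planned accrual, simulated false positives for the change score were 5.1-5.4%.

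**Step 5: what larger figures require.** Suppose exactly half the sample has both network and outcome shifted, so that C = 0.25·d_x·d_y. At 0.8 / 0.6 SD, C = 0.12, r = 0.12/√(1.16 × 1.09) = 0.107 and r√80 = 0.955. The rate is about 16%, and simulation runs gave about 15-17%. For visits the same split gave rate ratios of 1.07-1.09 and false positives of about 6-9% at the two larger shifts. Planned accrual does not produce this split.

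**The case against.** The strongest objection is that the straddle is unproven. The timetable is a plan. Data collection was due to end in March 2021, but the revised SAP is dated January 2022, so planned accrual is weak evidence of actual accrual. The SAP describes one intervention for everyone, beginning by telephone. Its mention of a home visit may mean only the earlier plan or usual practice. This stands, and it is why the remedy must be conditional.

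A reader might infer that participants received a mixture of home and telephone first contacts. Neither document says that anyone had a home visit. A reader might also infer that the trial cannot separate mechanism from period, or that false-positive rates near 17% should be expected. The documents do not support that either. The high rate needs half the sample shifted on both network and outcome, whereas on planned accrual only about 18 of 80 have a shifted change score. That result assumes a single drop, and a drop that kept deepening would distort the change score more.

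Two further points stand. In the dyadic GEE, the listed covariates are examples, so period is unspecified rather than excluded. Contrasts between network members there are mostly within one respondent at one date, so period matters much less. Period is also only one omission from the patient-level GLMs, which name neither arm nor baseline outcome. That does not remove the need for a period term, because the SAP itself singles out the pandemic as having changed the study.

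**Conclusion.** The point holds as a conditional gap in the patient-level GLMs. These are comparisons between caregivers on non-randomised network measures, the SAP documents pandemic-driven changes, and planned accrual would cross March 2020. If actual enrolment did so, a common period shift could be read as a network association.

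On planned accrual the size is negligible for the 0-3-month change score (about 5%). It is small for level measures of composition or engagement (about 5-9%, up to about 12% only with equal 0.8 SD shifts). If everyone falls in one homogeneous period, the bias is zero. These figures rest on assumed shifts, an assumed mid-March start, a one-time drop, one network measure per model and 80 analysable caregivers. Several correlated measures or other link functions would change the size.

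**What to change.** - State actual first and last enrolment dates and the range of dates for each assessment.
- If they straddle the pandemic, add a pre-specified period term (follow-up wholly before, straddling, or wholly within) to every patient-level network GLM. State the cut-off date used.
- In that case, also report network measures, burden and emergency care use by period and arm.
- If all participants fall in one period, say so and omit the term.
- In the dyadic GEE, treat period as an optional respondent-level covariate.

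The cost is a few sentences in the SAP and one or two degrees of freedom per model. No new data are needed, since the Recruitment Log (Protocol section 12.5 and Appendix C) has a date field and assessment dates should already be in the study's tracking records.

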1.0 Introduction

The overall goal of this study is to minimize negative consequences of Alzheimer's disease and related disorders (ADRD) diagnosis by enhancing the support systems of affected families through the provision of the Options Counseling-Health Education (OC-HE) intervention.

The primary objective is to evaluate the impact of OC-HE intervention on caregivers (caregiver burden) and patients (use of emergency care). The secondary objective is to evaluate the impact of the program through the proposed mechanisms of influence, enhanced social network composition (e.g., network size) and functioning (e.g., social support). In addition, we will assess intervention feasibility and acceptability to better understand intervention impacts and to inform future implementation from the perspectives of the participants, OC-HE interventionist, clinical care staff, and administrator at the Area Agency on Aging.

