7.0 Study Intervention

Intervention Description

The intervention consists of two parts, Options Counseling (OC) and Health Education (HE). The OC part includes family assessment, counseling and provision of emotional support, access assistance, and development of independent-living plans (care plans) using the Iowa's Heritage Area Agency on Aging database. The HE part includes post-diagnosis family education. Options Counselor (OC) is trained to implement these tasks through using motivational interviewing techniques. We developed seven modules of the HE toolkit based on an extensive literature review on unmet needs of families receiving diagnosis of dementia, experiences of Options Counselors, and expert reviews by experienced staff members at the local Alzheimer's Association.

Through the OC-HE intervention, we aim to minimize caregiver burden through enhancing the social support network system of the participants by providing direct access to community-based programs as well as to the Options Counselor who provides emotional support and instructions on how to form strong support networks. Lower burden and better support are associated with better patient outcomes, thus, we will also evaluate whether PWDs whose caregivers receive OC-HE intervention would use emergency or urgent medical services to a lesser extent.

Each intervention encounter will occur in a setting of the participant's choosing. Typically, the initial visit is in the home of the participant (caregiver) and involves just the participant and the Options Counselor. However, the participant is able to invite whomever they choose to come to the meeting, including the PWD. The participant may choose to have the meeting at different location if the person they are caring for lives with them and they do not want to introduce the information in this manner. Although it is preferable to have this initial visit in person, the meeting can be done via phone call or virtually through a web-conferencing if participant desires so. Normally, each home visit, or face to face meeting, lasts around 1.5 hours, however, because of the addition of the Health Education component in this particular study, we

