Mechanisms of Influence. The social network framework highlights the importance of enhancing network functions (e.g., social support) on health outcomes. Strong social support networks have been shown to be important for the well-being of caregivers and care recipients, and their ability to remain in the community. The intervention provides families 1) tangible, informational, and emotional support, 2) guidance on building strong support systems and effective communication, and 3) access service linking families directly to community-based resources. Through these activities, we intend to strengthen families' social networks to facilitate successful community living. In our prior study, families considered formal providers as important members of their caregiving support systems, suggesting the important role Area Agency on Aging staff can play in this mechanism. In this study, we are systematically examining the compositional and functional characteristics of social networks, that are theorized to influence patient and family outcomes. We will assess the mechanisms of influence using the social network measures specifically developed for dementia caregiving studies that assess social interactions specific to caregiving in addition to general support. Understanding the mechanisms through which intervention improves outcomes will provide a framework to optimize support for patients and their families across all stages of the illness.

Revised Data Analysis Plan

Network composition: Network members are enumerated based on participation in caregiving activities and provision of support to caregivers at baseline. In 3- and 6-month assessments, participants indicate changes in their networks (e.g., indicate those who are no longer part of support network, add new support providers). We will develop network composition measures including network size and proportion/number of family, non-family/friends, professional providers, live locally, gender, age groups (e.g., same/older/younger generations).

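### The network roster has no rule for the study's own Options Counselor, so the plan cannot separate receiving the intervention from a change in the rest of the caregiver's network

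*SAP*

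**What the plan says.** **Roster.** The SAP (Revised Data Analysis Plan, Network composition) states: "Network members are enumerated based on participation in caregiving activities and provision of support to caregivers at baseline". At 3 and 6 months caregivers report who has left and can "add new support providers". The derived measures include "network size and proportion/number of family, non-family/friends, professional providers". Under Perceived support, each member's functions are recorded by type, emotional and informational among them, and averaged within family, non-family and professionals.

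**Role of the counselor.** The SAP (Mechanisms of Influence) reports from a prior study that "families considered formal providers as important members of their caregiving support systems". It reads this finding as "suggesting the important role Area Agency on Aging staff can play in this mechanism". Protocol 7.0 expects burden to fall through a better support network, with direct access to community programs "as well as to the Options Counselor who provides emotional support and instructions on how to form strong support networks".

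**Who gets one.** Protocol 6.0 and 7.0 offer controls contact with a counselor only once the 6-month interview is done.

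**Objective and models.** Protocol 1.0 makes it a secondary objective to evaluate impact through "enhanced social network composition (e.g., network size) and functioning (e.g., social support". The SAP regresses caregiver and patient outcomes on composition measures, and 6-month outcomes on baseline-to-3-month change in network functions. It adds dyad-level logistic models fitted by GEE. None of these names study arm as a term, and no comparison of network measures between arms is written.

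No text shown flags, excludes or separately counts the interventionist. The baseline interview (Protocol Appendix L) is not reproduced.

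**The concern.** A caregiver who follows the roster rule correctly can list the counselor as a new professional supporter. That person is supplied by the study, to one arm, and delivers emotional and informational support, which are two of the functions being scored. Under the SAP's 3-month schedule the contacts fall inside the baseline-to-3-month window whose change scores predict the 6-month outcomes.

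Two things are at stake. First, a larger network in the intervention arm could mean that families gained other supporters, or only that they reported the study's calls. The planned measures do not tell these apart. Second, with no arm term, a network change driven by the counselor partly carries treatment assignment. A burden effect that runs through another route, such as education, could then appear as a network effect.

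**Working it through.** **1. The plan's own figure.** Protocol 5.0 gives 106 enrolled, 25% attrition, 80 analysed (40 per group) and about 84% power for a 4-point fall in burden. Attrition: 106 × 0.75 = 79.5, which agrees with 80. The 84% cannot be checked because no SD is given. Solving for it, SD = 4 / [(1.960 + 0.994) × √(2/40)] = 6.05 (two-sided 5%), or 4 / [(1.645 + 0.994) × √(2/40)] = 6.78 (one-sided 5%). No power figure is given for network measures. The burden SD below (6.06) is this back-solved two-sided value.

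**2. What one named counselor does.** Take a network of N members, P of them professionals and F family.
- Size goes from N to N + 1, and professionals from P to P + 1.
- Family and non-family counts, and the support averages within those classes, do not change.
- The family proportion falls from F/N to F/(N + 1).
- The professional support average rises if the counselor scores above the existing professionals and falls if below.

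If a share q of the intervention arm names the counselor, mean size there rises by q.

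**3. Arm comparison of size change.** Assumptions not in the documents: q; the SD s of size change; two-sided 5%; no other network change. With 40 per arm, the averaged SD is √(s² + q(1 − q)/2). The chance of significance is about Φ(q / [SD × √(2/40)] − 1.96). For q = 0.5 and s = 2: SD = √(4 + 0.125) = 2.03, standard error 0.454, ratio 1.10, Φ(−0.86) = 19.5%. Simulation (4,000 runs per cell) gives:

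| q | s = 1 | s = 2 | s = 3 |
|---|---|---|---|
| 0.25 | 18.8% | 8.2% | 6.5% |
| 0.50 | 53.6% | 19.5% | 12.0% |
| 0.75 | 88.5% | 36.5% | 19.4% |
| 1.00 | 99.1% | 60.3% | 30.5% |

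With the counselor left out of the count, the rate is 4.5% to 5.4%. The s = 1 column is the more relevant one for narrow measures such as the number of professionals.

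**4. Outcome regressed on network change, no arm term.** Burden falls 4 points in the intervention arm by a route unrelated to the network, with residual SD 6.06 and 3,000 runs per cell. Share of runs with a significant network coefficient:

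| q | s = 1 | s = 2 | s = 3 |
|---|---|---|---|
| 0.50 | 10.4% | 6.6% | 5.6% |
| 0.75 | 14.8% | 8.1% | 6.2% |
| 1.00 | 24.5% | 9.9% | 7.8% |

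The simulation error around 5% is √(0.05 × 0.95/3000) = 0.4 points, so 5.6% is hardly distinguishable from nominal. If the 4 points per 3-month period are read as 2 × 4 = 8 by 6 months, the ranges are 6.6% to 19.9% at q = 0.5 and 12.1% to 61.8% at q = 1. Across both burden effects, keeping the counselor and adding arm gives 4.5% to 5.6%; excluding the counselor without adding arm gives 4.4% to 5.8%.

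This is a simplification: one network predictor (size change) and a linear model. The SAP enters sets of measures and does not say at which assessment composition is taken. Baseline composition would not be affected.

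**The case against.** The strongest reply is that the counselor is an intended pathway. Both documents put agency staff inside the mechanism, so a caregiver who gains a counselor has gained a supporter. On the measure as the SAP defines it, a significant size difference would then be a correct finding. This stands. A reader might infer that any network effect in this trial would be spurious; the documents do not support that. What remains is that the plan offers no way to say which kind of change occurred.

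A reader might also infer that the intervention arm's network and support scores must rise. They need not. The rise depends on caregivers naming the counselor, and Appendix L may carry an instruction about study staff. Support is averaged within class and can move either way. The SAP already separates family, non-family and professionals, so a gain made up only of the counselor would leave family and non-family counts alone. But the professional class still mixes the interventionist with the community services that the program is meant to open up.

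Three further points stand in part.
- Caregivers can remove members, and under the SAP schedule the calls end at 3 months, so the effect may shrink by 6 months.
- Protocol Appendix A describes options counseling as a service the agency must provide, and nothing shown bars controls from seeking it. Only the study's own supply is confined to one arm.
- The proxy problem arises more directly from the missing arm term, and adding that term removes it in the simulation even with the counselor kept.

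**Conclusion.** The concern holds as a gap in separation. As written, the roster can include an interventionist whom the study supplies to one arm only before the last survey. Size and number of professionals then rise by one for each caregiver who names that person, and no rule lets the analyst set this apart. With no arm term named, counselor-driven change can act partly as a proxy for arm.

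The size is unknown, because the documents give neither a naming share nor an SD for network change. The 7-99% range spans q from 0.25 to 1 and s from 1 to 3. It applies to a comparison that the secondary objective implies but the SAP does not write. It should not be read as the type I error of a planned test. For a simple version of the written models at a 4-point burden effect, the excess over 5% is slight at 50% naming (about 6-10%) and moderate at 100% (8-25%). The problem is small if few caregivers name the counselor or if networks vary widely.

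**What to change.** - Identify the study interventionist in the roster. The SAP is dated January 2022 and the protocol planned to finish data collection by March 2021, so this may mean coding from recorded names or relationships. Mark other Options Counselors in either arm too, so that dropping only the study's own can be seen for what it is.
- Report network size, number and proportion of professionals, the other proportions with the same denominator, and professional support, each with and without the interventionist.
- Describe the version with the counselor as including the intervention itself. Claim change in the family's other network only from the version without. Neither version need be the sole basis for the mechanism; that is a choice of estimand and should be stated.
- Add study arm to the GLM and GEE models.
- If Appendix L already tells interviewers how to treat study staff, cite that rule in the SAP.

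The cost is a second set of derived variables and results, one more model term, and possibly retrospective coding.
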